14.2 Device Accountability

14.2.1 Receipt of Study Device

The contents should be examined upon receipt to ensure packaging and labeling is intact and the devices have not been damaged. Any damage should be immediately reported to the Sponsor.

14.2.2 Storage

The device and disposables should be stored in a dry place at room temperature. Proper care should be taken to ensure that the study inventory will not be damaged.

14.2.3 Accountability

The Trima Accel device, disposables, arm cuff, InterSol solution, and software will be provided by Terumo BCT for use in this study. The Trima Accel disposables and InterSol solution are FDA cleared and marketed in the United States.

15 STATISTICAL PLAN

The following section summarizes the statistical methods that will be used in the analysis of the clinical data from this active-controlled trial. Continuous variables will be described using means, medians, and measures of dispersion including standard deviation and ranges with categorical variables will be summarized with frequencies and percentages.

15.1 Sample Size

As specified in the FDA guidance, for up to 1 allowed failure, 93 platelet products are required to show that the proportion of platelet units with an acceptable residual WBC level is at least 95% with 95% confidence.⁹ With 93 platelet products being collected, 16 failures or fewer is required to show that the proportion of platelet units with an acceptable platelet yield is at least 75% with 95% confidence.

15.2 Outcome Measures

15.2.1 Primary Endpoint

The primary endpoint for this study is the proportion of platelet units with an acceptable residual WBC level. Counts and percentages of success rates and the lower one-sided 95% exact binomial confidence intervals will be calculated separately for success rates of single, double, and triple platelet products. If 0 or 1 failure is observed, then the confidence interval will suggest that the true success rate is at least 95% with 95% confidence for the given platelet product. This approach will be applied independently to single, double, and triple platelet products.

15.2.2 Secondary Endpoint

The secondary endpoint of platelet yield will be summarized for single, double, and triple platelet products. Separately for single, double, and triple platelet products, the lower one-sided 95% exact binomial confidence intervals will be calculated for the proportion of platelet units with an acceptable platelet yield. If 16 or fewer failures are observed, then the confidence interval will suggest that the true success rate is at least 75% with 95% confidence for the given platelet product.

15.2.3 Safety Measures

Adverse events will be summarized by the medical dictionary for regulatory activities (MedDRA Version 18.1 or later). Tables will describe the frequency and percentage of all AEs, SAEs, and UADEs reported by subjects in the safety population. Presentations will summarize AEs by maximum reported severity and relationship to device and procedure. AEs leading to study or procedure discontinuation will also be tabulated.

15.3 Analysis Populations

The safety population will include of all subjects enrolled in this trial for whom at least 1 apheresis procedure is initiated. The Full Analysis Set (FAS) will be defined separately for single, double, and triple platelet products. The FAS for a given platelet product will consist of the first 93 collections that do not meet any of the protocol exclusion criteria described in Section 15.4. The FAS will be used to examine the primary and secondary endpoints.

15.4 Protocol Analysis Exclusions

Data points will be excluded from analysis in the following situations:

1. Inability to collect a complete unit due to:
 - a. Subject issues (inadequate access, reaction, needle abort, procedure disqualification upon Trima Accel device update of subject platelet count and hemoglobin or hematocrit).
 - b. Decision to stop procedure by subject, Investigator, nursing staff or operator.
 - c. Equipment failure or malfunction (unrecoverable system failure; plugged or malfunctioning filter[s]).
 - d. Protocol deviation.
2. Decision to stop the procedure due to a change in the subject platelet count (ie subject qualifies for double, however day-of platelet count is for a single platelet product and 93 single platelet products have already been collected).
3. Failure or inability to update the Trima Accel system with the actual platelet count (platelet count performed on sample taken from Trima Disposable sample pouch) AND the actual platelet count differs from the entered platelet count by more than 10%. Updating the Trima Accel system with actual platelet count from the sample pouch is standard procedure for the Trima Accel system.
4. Incomplete or incorrect collection procedure or post-collection processing that affects the primary or secondary endpoint due to:
 - a. Equipment failure or malfunction.
 - b. Subject issues (inadequate access, reaction, needle abort).
 - c. Unanticipated centrifuge stop during collection procedure.
 - d. Failure to follow collection or post-collection handling procedure outlined in the Trima Operator's Manual, and supplement(s).
 - e. Subject and procedure samples are not taken as specified in protocol.
 - f. Solution other than InterSol added to platelets prior to storage.
 - g. Results of endpoint assays are not available.

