Study Title:	Evaluation of the Performance of Trima Accel [®] Version 7.0 Software Enhancements for the Collection of Platelets Stored in Platelet Additive Solution	
CIP #:	CTS-5059	
CIP Version / Date:	Version 4.0/22 NOV 2016	
Replaces CIP Version / Date:	Version 3.0/19 FEB 2016	
Rationale:	This amendment was made to increase the number of healthy adult subjects enrolled in this study from up to 350 subjects to up to 450 subjects. After study initiation, it was noted that the number of screen failures and procedures excluded per Section 15.4 Protocol Analysis Exclusions was higher than originally anticipated. Therefore, in order to ensure 93 evaluable single, double, and triple products are collected from 279 individual subjects, the total number of subjects enrolled in the study will be increased from up to 350 to up to 450. Additionally, typographical error corrections, sponsor contact information, and minor wording changes for clarity have been made and will not be reflected in the table below.	
Section(s)	Used to Read:	Now Reads:
Synopsis, Section 8.1 Study Design, and Section 9.1 Number of Subjects and Selection	Up to 350 healthy adult subjects will be enrolled in this study to ensure 93 single, 93 double and 93 triple platelet product evaluable data points	Up to 450 healthy adult subjects will be enrolled in this study to ensure 93 single, 93 double and 93 triple platelet product evaluable data points

SYNOPSIS

Sponsor:	Terumo BCT, Inc.
Study Title:	Evaluation of the Performance of Trima Accel [®] Version 7.0 Software Enhancements for the Collection of Platelets Stored in Platelet Additive Solution
Study Number:	CTS-5059
Target Population:	Healthy Adults
Device Description:	
The Trima Accel system is an automated blood component collection system that uses centrifugal force to separate donor blood into platelet, plasma, and red blood cell (RBC) components and uses Anticoagulant Citrate Dextrose, Solution A (ACD-A) as the anticoagulant. The device is comprised of three major sub-systems, 1) the Trima machine itself, 2) sterile, single-use disposable blood tubing sets and, 3) embedded software. There are additional optional accessories such as plasma bags, platelet bags, a seal safe system, and barcode scanner kit.
 
The Trima Accel system received United States Food and Drug Administration (FDA) 510(k) clearance for hyperconcentrated platelet collections stored in platelet additive solution (PAS) on 17 December 2012 (BK120049).

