9.4 Enrollment

A donor is considered to be an enrolled subject following informed consent. It is expected that due to the screening and eligibility requirements, some fraction of subjects will not qualify for a platelet/plasma donation after consent and some who are enrolled may not complete their anticipated procedures. Subjects will be considered screen failures if they fail to meet any of the eligibility criteria, and subjects who do not complete their anticipated procedure (after venipuncture) will be considered as a study procedure discontinuation/termination.

After informed consent has been obtained, subjects will receive a unique study identification (USID) number. The USID number will use the following convention: 59XX-YYY, where XX is the pre-assigned site number and -YYY will be a sequential number starting with 001. The USID number will be recorded on the electronic Case Report Form (eCRF).

Subjects that fail screening criteria on information or laboratory values that are anticipated to change, may be rescreened. Subjects that have incomplete procedures or donated a product that meets any of the protocol analysis exclusions (Section 15.4) may rescreen if they meet all

inclusion criteria when they return. Subjects that are rescreened will be assigned a new USID number.

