11 LABORATORY TESTS

Laboratory tests will be analyzed locally at each study site. Copies of the current laboratory certifications and normal ranges will be provided to Terumo BCT prior to start of the study and upon every renewal throughout the duration of the study.

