### 3.2 Study Populations

Analysis populations for this clinical investigation will be the Full Analysis Set (FAS) and Safety Populations.

For all analyses by platelet product, the platelet product type (single, double, triple, or unassigned) will be determined from the calculated platelet yield (see Section 3.3) using the following.

- If the platelet yield, rounded to the nearest tenth, is  $\geq 9.3 \times 10^{11}$ , then the product will be analyzed as a triple.
- Otherwise, if the platelet yield, rounded to the nearest tenth, is  $\geq 6.2 \times 10^{11}$ , then the product will be analyzed as a double.
- Otherwise, if the platelet yield, rounded to the nearest tenth, is  $< 6.2 \times 10^{11}$ , then the product will be analyzed as a single.
- Otherwise, if the procedure was not started, not completed or the platelet yield could not be determined for some other reason, as per the protocol analysis exclusion criteria, then the subject will be analyzed as “Unassigned”.

The Safety Population will include all subjects enrolled in this trial for whom at least 1 apheresis procedure is initiated. A procedure will be considered to have been initiated if a Trima procedure start date and time are present. The Safety Population will be used for all summaries except the primary and secondary endpoints and the derived apheresis related parameters.

Due to the design of the study, a given subject may be enrolled in the study on multiple occasions. These subjects may also qualify for the Safety Population more than once. If this occurs, the subjects will be analyzed separately for each enrollment.

The Full Analysis Set (FAS) will be defined separately for single, double, and triple platelet products and will not include any repeat subjects. The FAS for a given platelet product will consist of all collections that do not meet any of the exclusion criteria specified below. The FAS will be used to examine the primary and secondary endpoints and the derived apheresis related parameters.

Data points will be excluded from the FAS analysis in the following situations:

1. Inability to collect a complete unit due to:
  - a. Subject issues (inadequate access, reaction, needle abort, procedure disqualification upon Trima Accel device update of subject platelet count and hemoglobin or hematocrit).
  - b. Decision to stop procedure by subject, Investigator, nursing staff or operator.

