- c. Equipment failure or malfunction (unrecoverable system failure; plugged or malfunctioning filter[s]).
  - d. Protocol deviation.
2. Decision to stop the procedure due to a change in the subject platelet count (i.e. subject qualifies for double, however day-of platelet count is for a single platelet product and 93 single platelet products have already been collected).
  3. Failure or inability to update the Trima Accel system with the actual platelet count (platelet count performed on sample taken from Trima Disposable sample pouch) AND the actual platelet count differs from the entered platelet count by more than 10%. Updating the Trima Accel system with actual platelet count from the sample pouch is standard procedure for the Trima Accel system.
  4. Incomplete or incorrect collection procedure or post-collection processing due to:
    - a. Equipment failure or malfunction.
    - b. Subject issues (inadequate access, reaction, needle abort).
    - c. Unanticipated centrifuge stop during collection procedure.
    - d. Failure to follow post-collection handling procedure outlined in the Trima Operator's Manual, and supplement(s).
    - e. Subject and procedure samples are not taken as specified in protocol.
    - f. Solution other than InterSol added to platelets prior to storage.
    - g. Results of endpoint assays are not available.

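### Exclusion for a procedural error depends in the Protocol on whether the error affected the endpoint, in the SAP it does not, and neither document has the decision made blind to the result

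*Protocol*

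**What the plan says.** Protocol 15.4 lists four grounds for leaving a data point out of the analysis. Item 4 applies to "Incomplete or incorrect collection procedure or post-collection processing that affects the primary or secondary endpoint due to" causes 4a to 4g. These are equipment failure, subject issues, an unplanned centrifuge stop, handling that departs from the operator's manual, sampling departures ("Subject and procedure samples are not taken as specified in protocol"), a solution other than InterSol, and missing assay results. Items 1 to 3 carry no condition about the endpoints.

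SAP 3.2, item 4, reads "Incomplete or incorrect collection procedure or post-collection processing due to" and gives the same causes, except that 4d covers post-collection handling only. The condition about the endpoints is absent. The SAP does not mention the difference or say which text governs.

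Exclusion leads to replacement. Protocol 8.1 calls a completed product evaluable if no 15.4 exclusion applies, and sizes enrolment to reach 93 evaluable products of each type. Protocol 15.3 states: "The FAS for a given platelet product will consist of the first 93 collections that do not meet any of the protocol exclusion criteria". The SAP version is: "The FAS for a given platelet product will consist of all collections that do not meet any of the exclusion criteria specified below". Under Protocol 9.4, a donor who "donated a product that meets any of the protocol analysis exclusions (Section 15.4) may rescreen".

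The study is open-label (Protocol 8.1). On the endpoint assays, Protocol 11 says: "Laboratory tests will be analyzed locally at each study site". Neither document names who assigns an exclusion, when this happens relative to the assay, or what that person may know.

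**The concern.** Whether an error affected the WBC count or the yield is, on the ordinary reading, a question about the measured value. Suppose two products have the same handling error. The one with a high WBC count looks affected and is excluded; the one with a low count looks unaffected and stays as a success. The stated 95% confidence assumes that inclusion does not depend on the outcome.

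The primary rule leaves little room for such selection, because it allows one failure in 93. The amendment rationale at the front of the Protocol also shows that exclusions are a practical matter here: it reports that "the number of screen failures and procedures excluded per Section 15.4 Protocol Analysis Exclusions was higher than originally anticipated".

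**Working it through.** **Inputs.** From Protocol 15.1 and 15.2.1 and SAP 3.7.3: n = 93 per product type, at most 1 WBC failure, one-sided 95% exact (Clopper-Pearson) lower limit, target 95%. The share of failing products removed under item 4 is not in the documents and is assumed below. The figures are for the WBC endpoint and one product type.

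**1. The plan's own figure.** With x failures in n, the lower limit is the 5% quantile of a Beta(n − x, x + 1) distribution.

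| n | failures | lower limit | result |
|---|---|---|---|
| 93 | 0 | 96.83% | pass |
| 93 | 1 | 95.0006% | pass |
| 93 | 2 | 93.38% | fail |
| 92 | 1 | 94.95% | fail |

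So 93 is the smallest number that allows one failure, as the plan says. At a true failure rate of 5%, the chance of passing is 0.95^93 + 93 × 0.05 × 0.95^92 = 0.0085 + 0.0415 = 0.0500.

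**2. At most one failing product discarded and replaced.** The first failing product is dropped and the next collection takes its place. The type then passes if the first 94 collections contain at most 2 failures. With Binomial(94, 0.05), P(0) + P(1) + P(2) = 0.0081 + 0.0398 + 0.0975 = 0.1454. The false-pass probability rises from 5.0% to 14.5%.

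**3. A share q of failing products removed, all passing products kept.** The failure rate among analysed products becomes g = f(1 − q)/(1 − fq), with f = 0.05. The pass probability is P(X ≤ 1) for Binomial(93, g).

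| q (assumed) | g | false-pass probability |
|---|---|---|
| 0 | 0.0500 | 5.0% |
| 5% | 0.0475/0.9975 = 0.0476 | 6.0% |
| 10% | 0.0450/0.9950 = 0.0452 | 7.3% |
| 25% | 0.0375/0.9875 = 0.0380 | 12.8% |

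If exclusion does not depend on the result and the errors are unrelated to outcome, q = 0 applies and the probability stays at 5.0%.

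**4. Which items are exposed.** 4c (centrifuge stop) and 4f (wrong solution) are largely matters of fact. 4g (no result) cannot be chosen on the result. 4a, 4b, 4d and 4e need a judgement on whether something went wrong and whether it mattered. That is where knowledge of the count could enter.

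**The case against.** - **The SAP does not contain the condition.** Read literally, SAP 3.2 removes passing and failing products with the same error alike. This stands: the asymmetry follows from the Protocol alone. It does not close the gap. The SAP claims no precedence, Protocol 15.4 governs evaluability and rescreening, and under either text an error can still be declared with the result in hand.
- **Affecting the endpoint may mean being of a kind that could affect it.** That reading is possible and would weaken the selection. The Protocol does not say which is meant.
- **The grounds are narrower than they look.** 4d is limited to collection and post-collection handling, and in the SAP to post-collection handling. Protocol 10.2.3 sets no sampling time for the product, so 4e cannot be breached on that point. Both hold, and they limit the scope.
- **There is some transparency.** Deviations go to the sponsor (Protocol 13.8), eCRF data are checked against source (Protocol 16.4.2), and all eCRF data are listed (SAP 3.7). The SAP also keeps repeat subjects out of the FAS. Silent removal is therefore harder, but listings do not make the decision blind, and replacement does not need the same donor.
- **The shares are assumed.** This is correct. A reader might take the gap between 450 enrolled and 279 evaluable (171) as a measure of item 4 exclusions. It is not, because it also covers screen failures and incomplete procedures (Protocol 8.1).

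**Conclusion.** The concern holds in a limited form. The two documents define item 4 differently, the Protocol version can be read as depending on the measured result, and nothing keeps that result from whoever decides. One result-driven exclusion is enough to turn a fail (2 in 93) into a pass (1 in 93). At a true failure rate of 5%, discarding and replacing at most one failing product raises the false-pass probability for a product type from 5.0% to 14.5%. Removal of a small share has a modest effect (6.0% at 5%, 7.3% at 10%); at 25% it is 12.8%.

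These figures assume independent products, every passing product retained, and a true rate exactly at the limit. A reader might infer that failing products were removed, or that sites make the call after seeing the count. The documents support neither: they give no count of item 4 exclusions and do not say who decides. What they show is an opportunity for bias without a safeguard. Its actual size is unknown.

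**What to change.** 1. Reconcile Protocol 15.4, item 4, with SAP 3.2, item 4, including the scope of 4d. Exclusion should depend on a documented event of a kind that can affect the endpoint, not on the measured value.
2. State in both documents that sponsor staff without access to the WBC and yield values assign and date each item 4 exclusion.
3. Add one sensitivity table of the primary endpoint, by product type and with the same exact lower limit, that restores every completed product with a WBC result otherwise excluded under 4a to 4e. Leave out 4f, which is not the study product, and 4g, which has no result.

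The cost is wording in two documents, masking two fields during the exclusion review, and one table. In that table some products with genuine handling errors will count as failures. Because the study has already started, reconciling the lists may also reclassify a few products already counted as evaluable.

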6 RATIONALE FOR THE CURRENT STUDY

The study is designed to evaluate changes to the Trima Accel software (Version 7.0) to ensure they meet the FDA acceptance criteria for leukoreduction^{9,10} ($< 5.0 \times 10^6$ WBC per transfusable unit) and results in platelet yields $\geq 3.0 \times 10^{11}$ for singles, $\geq 6.2 \times 10^{11}$ for doubles and $\geq 9.3 \times 10^{11}$ for triples.

The operating range for the system flow rates, anti-coagulant ratios, storage conditions, and centrifugal forces are the same as the currently FDA cleared Trima Accel system. There are no

changes to the environment or storage conditions for platelets therefore no platelet quality data will be evaluated. Additionally, no products will be transfused from this study.

The Trima Accel system Version 7.0 software is intended to consolidate multiple enhanced software versions with the additional value of creating improvements relevant globally. This effort will yield a software release with several new enhancements targeted at improving productivity, leukoreduction and WBC flagging, reducing procedure time, reducing venous access alarms, and improving the user and donor experience.

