#### 3.7.3 Efficiency Analysis

##### Primary Endpoints

##### Primary Endpoint Acceptance Criteria

Parameter	Measured	Acceptance Criteria
Residual WBC Count – Single Unit	Flow cytometry; BD Leukocount™ or equivalent	Residual WBC count is $< 5.0 \times 10^6$
Residual WBC Count – Double Unit	Flow cytometry; BD Leukocount or equivalent	Residual WBC count is $< 8.0 \times 10^6$ or each component $< 5.0 \times 10^6$
Residual WBC Count – Triple Unit	Flow cytometry; BD Leukocount or equivalent	Residual WBC count is $< 12.0 \times 10^6$ or each component $< 5.0 \times 10^6$

Abbreviations: WBC = white blood cell.

Summary statistics will be provided separately for single, double, and triple residual WBC levels. The summaries will include N, mean, standard deviation, median, minimum, and maximum.

Frequencies and percentages of platelet units with an acceptable residual WBC level and the lower one-sided 95% exact binomial confidence intervals (Clopper-Pearson) will be calculated separately for single, double, and triple platelet products. If the lower one-

sided confidence interval is greater than 95%, then it will be concluded that the proportion of platelet units with an acceptable residual WBC level is at least 95% for the given platelet product.

Secondary Endpoints

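### Completed, assayed products from runs with a malfunction or centrifuge stop are left out of the endpoint analysis, under an item 4 that the Protocol and SAP word differently

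*Protocol*

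**What the plan says.** Protocol 15.3 and SAP 3.2 make the Full Analysis Set (FAS) the only population for the WBC and yield endpoints. Two groups of exclusions concern the device.

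- Item 1c covers equipment failure where no complete unit could be collected.
- Items 4a and 4c cover equipment malfunction and "Unanticipated centrifuge stop during collection procedure". Item 4 does not require that the unit be incomplete, so it can reach a finished product with a WBC result.

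The opening line of item 4 differs between the documents. Protocol 15.4 reads "Incomplete or incorrect collection procedure or post-collection processing that affects the primary or secondary endpoint due to". SAP 3.2 reads "Incomplete or incorrect collection procedure or post-collection processing due to".

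Protocol 15.3 takes the first 93 non-excluded collections of each type, so an excluded collection is replaced. SAP 3.2 takes all non-excluded collections.

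The success rule is in Protocol 15.1: "for up to 1 allowed failure, 93 platelet products are required to show that the proportion of platelet units with an acceptable residual WBC level"; the target is 95%, to be shown at the 95% confidence level. If the lower limit exceeds 95%, SAP 3.7.3 states "then it will be concluded that the proportion of platelet units with an acceptable residual WBC level is at least 95" percent for that product type. Neither document plans a WBC or yield analysis that includes the excluded products.

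**The concern.** Protocol section 6 gives the purpose as evaluating the Version 7.0 software. Section 2.1 lists changes to pump speed during prime, LRS chamber clearing, the platelet collection algorithms and the operating system. A malfunction or an unplanned stop may therefore be a consequence of what is being tested. If such a run still yields a complete product, its WBC count bears on the question, yet it is left out. The SAP conclusion is worded for platelet units of the given type, without restriction to runs free of malfunction.

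The Protocol's condition adds a second problem. Read literally, a malfunction run with a good WBC count has not affected the endpoint and stays, while one with a high count goes. The study is open-label (Protocol 8.1), laboratory tests are run at each site (section 11), and nothing says that exclusions are settled before results are known. With a rule that allows one failure, a few such decisions could determine whether a product type passes.

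**Working it through.** **Inputs.** n = 93 per product type, at most 1 failure, target 95% (Protocol 15.1). One-sided 95% exact limit for each type separately (Protocol 15.2.1), Clopper-Pearson, pass if the limit exceeds 95% (SAP 3.7.3). For yield, at most 16 failures in 93 against 75% (Protocol 15.1). Malfunction, centrifuge-stop and exclusion rates are not given.

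**1. The plan's own figure.** With f failures in n, the lower limit L solves P(at most f failures | n, success probability L) = 0.05. Equivalently, L is the 0.05 quantile of Beta(n − f, f + 1).

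- 1 of 93: L = 95.0006%, pass. 1 of 92: 94.95%, fail. So 93 is the minimum, as stated.
- 2 of 93: 93.38%, fail.
- Yield: 16 of 93 gives 75.05%, pass; 17 of 93 gives 73.85%, fail.

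The stated sample size and both failure limits reproduce. The WBC rule has almost no slack.

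**2. Returning excluded products that have a failing WBC.** Suppose k completed, assayed products excluded under 4a or 4c had failing counts (k is assumed), and add them to a FAS of 93.

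| Failures in FAS | k | Total | Lower limit | Result |
|---|---|---|---|---|
| 1 | 0 | 1 of 93 | 95.001% | pass |
| 1 | 1 | 2 of 94 | 93.45% | fail |
| 0 | 1 | 1 of 94 | 95.05% | pass |
| 0 | 2 | 2 of 95 | 93.52% | fail |

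One returned failure changes the result if the FAS already has one. Two change it if the FAS has none. Returning a product with a passing WBC does no harm: a FAS with 1 failure plus one passing product is 1 of 94, again 95.05%.

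**3. Chance of a false pass.** Let the true success rate over all completed products be exactly 95%. Let a share s of failing units be excluded and replaced, with passing units kept. The success rate in the FAS becomes p = 0.95 / (1 − 0.05s), and the chance of passing is p^93 + 93 p^92 (1 − p).

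- s = 0: p = 0.9500, 5.0%
- s = 0.10: p = 0.95 / 0.995 = 0.9548, 7.3%
- s = 0.25: p = 0.95 / 0.9875 = 0.9620, 12.8%
- s = 0.50: p = 0.95 / 0.975 = 0.9744, 30.8%

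These shares are illustrative. If a share t of passing units is removed as well, p = 0.95(1 − t) / [0.95(1 − t) + 0.05(1 − s)], which returns to 0.95 when t = s. The inflation therefore arises only if failing units are removed more often than passing ones.

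**4. The two wordings applied to one case.** Take a completed run with a centrifuge stop that made the procedure incorrect.

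- Passing WBC and yield: kept under a literal reading of the Protocol, excluded under the SAP.
- Failing WBC: excluded under both.

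The analysis set, and the direction of any selection, depends on which document is followed.

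**The case against.** A reader might infer that no leukoreduction failure caused by the device can ever count. The documents do not support that. A completed run with no recognised malfunction, stop or procedural error is judged against the WBC limits. If the new algorithms or LRS chamber changes leukoreduce poorly in such a run, it is a failure. That is the main question of the study, and it is tested.

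A reader might also want every device-related exclusion counted as a failure. Item 1c gives no complete unit. The endpoint is a proportion of platelet units, and Protocol 8.1 defines evaluable as a completed product, so 1c is a matter of reliability. Counting runs without a result as WBC failures would change the endpoint. It also could not be done by product type, because SAP 3.2 sets the type from the calculated yield and calls runs that were not completed, or whose yield could not be determined, unassigned.

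The Protocol's condition has a milder reading: a fault of a kind that compromises the measurement, whatever the value found. Its use over items such as a wrong solution, missed samples and unavailable assays fits that reading, and the SAP text has no condition at all. So dependence on the result is a possible reading, not an established fact. It remains that the wording permits it and that the documents disagree.

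The size is uncertain. No malfunction rate is given, and the documents do not say whether a run can continue after a centrifuge stop. The reason for the amendment was more screen failures and exclusions than expected, but these are combined and given without counts or causes.

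Some information is kept elsewhere. Device deficiencies are reported (Protocol 14.1) and are a safety endpoint (SAP 3.6), eCRF data are listed (SAP 3.7), and reasons for discontinuation are tabulated (SAP 3.7.2). None of this enters the WBC or yield proportions, and SAP 3.7.5 names no deficiency table.

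**Conclusion.** The concern holds in a limited form. Completed, assayed products can be removed because of an equipment malfunction or centrifuge stop in a study of new device software. The Protocol's item 4 can be read as tying removal to the result, and the SAP's item 4 defines a different set. One or two excluded products with a failing WBC could change the conclusion for a product type; that follows from the plan's own rule. Whether any such product exists cannot be told from the documents.

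The rise in the false-pass chance from 5.0% to between 7.3% and 30.8% rests on assumed shares of 10% to 50% of failing units being removed while passing units stay. It shows sensitivity and is not an estimate. The planned FAS is defensible as the primary set. The gap should be closed before the analysis.

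**What to change.** 1. Keep the planned FAS as primary. Use one wording of item 4 in Protocol 15.4 and SAP 3.2, with no condition that depends on the endpoint result, and one statement of whether the FAS is the first 93 or all eligible collections.
2. State that exclusions are decided from the procedure record before WBC and yield results are seen, and that each decision and its date are recorded.
3. Add to SAP 3.7.3 a sensitivity analysis that includes completed, assayed products excluded under 4a or 4c at their measured WBC and yield. These products have a calculated yield, so the SAP 3.2 rule can assign their type. Protocol 9.4 lets a donor return after an excluded product, so say how a donor who appears twice is handled.
4. Tabulate all exclusions by reason and product type, including unassigned. Report 1c and unassayed runs descriptively, not as WBC failures.

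The cost is wording in two documents, the sensitivity analysis and one extra table. The sensitivity result may be less favourable than the primary.
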